## STUDY PLANS AND PROCEDURES

### Participants and Treatment Regimen

This is a prospective observational study of fifty postpartum women with a recent GDM pregnancy. All participants will be requested to return at 4-16 weeks postpartum for a 75 gm 2-hour OGTT as part of standard care after gestational diabetes. Fifty women with a history of GDM will be enrolled to use a blinded continuous glucose monitor (Dexcom G7). All CGM data will be masked and therefore not available to participants, clinicians, or researchers in real time. Participants otherwise will receive standard clinical care. All participants will be recruited from the Woman's Hospital Diabetes Clinic or from the maternal fetal medicine practice referring to the clinic. Those who wish to participate will provide written informed consent. The Woman's Hospital Institutional Review Board (WHIRB) will have approved both the protocol and consent.

All subjects will undergo a verbal screen, and if they are eligible and sign a medical release form, their medical records will be obtained to confirm their medical history. After consenting, demographic data, gravidity, parity, and body mass index (BMI) will be obtained. The patient's physician will be notified of participation in the study and have access to the laboratory results.

#### **Eligibility:**

##### **Inclusion criteria:**

- include diagnosis of gestational diabetes during recent pregnancy (4-16 weeks)
- age 18 or older.
- written informed consent

##### **Exclusion criteria:**

- pregestational diabetes (type 1 or type 2)
- include known known skin adhesive allergy which would prevent subject from wearing a CGM,
- history of bariatric surgery or other surgeries that induce malabsorption
- long-term use (>2 weeks) of systemic steroids during the testing interval
- inability or refusal to comply with protocol

For study participants, a Dexcom G7 CGM (Dexcom, Inc., San Diego, CA, United States) in blinded mode (participant unable to see the glucose values) will be worn for 10 days. Dexcom G7 CGM sensor measures interstitial glucose concentrations every 5 minutes. Insertion of the sensor will require an additional hospital visit for DEXCOM placement and women will be offered flexibility in scheduling to assist compliance. Trained research personnel will assist in implanting the sensors. Neither participants nor professionals will have access to the glucose measurements during sensor use. The Dexcom G7 sensors will be removed after 10 days and returned to study coordinator. All participants will receive a \$100 incentive for participation in the trial

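### Eligibility admits women already diagnosed with diabetes since delivery, or on a glucose-lowering drug at sensor placement, and the plan has no rule for their treated values

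*Combined protocol and SAP*

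**What the plan says.** Under Inclusion criteria the plan asks for three things: "include diagnosis of gestational diabetes during recent pregnancy (4-16 weeks" postpartum, age 18 or older, and written consent. None of these concerns glycemic status or treatment since delivery.

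Under Exclusion criteria there are five items. The one on diabetes is "pregestational diabetes (type 1 or type 2". The one on drugs is "long-term use (>2 weeks) of systemic steroids during the testing interval". The others are adhesive allergy, bariatric or malabsorptive surgery, and inability or refusal to comply.

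The section Participants and Treatment Regimen sets the surroundings:

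- Recruitment: "All participants will be recruited from the Woman's Hospital Diabetes Clinic or from the maternal fetal medicine practice referring to the clinic".
- Care: "Participants otherwise will receive standard clinical care".
- Baseline data: "After consenting, demographic data, gravidity, parity, and body mass index (BMI) will be obtained".
- Records: for eligible women who sign a release, "their medical records will be obtained to confirm their medical history".
- Results: "The patient's physician will be notified of participation in the study and have access to the laboratory results".

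The Study Objective places the OGTT, HbA1c and fructosamine tests within the 10 days of sensor wear. The section on HbA1c, fructosamine and OGTT data sorts women into normal, prediabetes and diabetes by measured glucose and HbA1c. Neither that section nor Statistical analysis mentions treatment.

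**The concern.** The study asks whether a CGM worn after childbirth can identify women at risk of diabetes, judged against the OGTT, HbA1c and fructosamine. That question belongs to women whose postpartum status is not yet known and whose glucose is not being lowered by a drug. The criteria do not restrict entry to such women.

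Two different problems follow.

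- **Known diagnosis, untreated.** Her values are valid, but she is not someone a screening test would be used on. Including her changes the case mix (spectrum) in which the CGM is judged.
- **On a glucose-lowering drug.** Her OGTT may read lower than it would untreated, so the reference label itself may be wrong. Her HbA1c may still reflect earlier weeks, so the tests can disagree because of treatment timing and not because of how well they perform.

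At stake is how the comparison can be read. If such women enrol, the planned data and analyses would not show who they are or how far they drive the result.

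**Working it through.** The plan gives no figure for this point, so there is none to reproduce. The check is first textual, then a small illustration of scale.

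**Step 1. Does any text close the gap?**

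| Place in the document | Acts on a diagnosis since delivery? | Acts on glucose-lowering drugs? |
|---|---|---|
| Inclusion criteria | No | No |
| Exclusion criteria | No; only diabetes before the pregnancy | No; only steroids beyond 2 weeks |
| Participants and Treatment Regimen | Records confirm history, but no rule follows | Medication not among the listed data |
| HbA1c, Fructosamine and OGTT data | No; measured values only | No |
| Statistical analysis | No | No exclusion, stratification or sensitivity analysis |

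The gap is open throughout. It is an omission: nowhere does the plan say that it means to include these women.

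**Step 2. Do the tests look back over the same period?** From the Background: HbA1c covers the preceding 2-3 months and fructosamine the preceding 1 to 3 weeks. The CGM covers 10 days. Taking a month as 52/12 weeks, 2-3 months is 8.7 to 13 weeks. A drug started a few weeks before placement would act on the whole CGM trace and on the OGTT, but on only part of the HbA1c window. Discordance from treatment timing is therefore possible.

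**Step 3. What would one such woman weigh?** Inputs: 50 women (Study Objective) and 30% persistent dysglycemia (Background). Expected abnormal women: 0.30 × 50 = 15. The number *k* who are treated and read as normal is not given; the values below are assumptions.

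| *k* (assumed) | Observed abnormal, (15 − *k*)/50 | Share of abnormal group lost, *k*/15 |
|---|---|---|
| 0 | 15/50 = 30% | 0% |
| 1 | 14/50 = 28% | 7% |
| 2 | 13/50 = 26% | 13% |
| 3 | 12/50 = 24% | 20% |
| 5 | 10/50 = 20% | 33% |

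For comparison, the Wilson 95% interval is 19.1% to 43.8% for 15/50 and 11.2% to 33.0% for 10/50. Sampling error on the proportion is thus at least as large as these shifts. The harm lies mainly in the labels of a small abnormal group.

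**Step 4. How likely is at least one such woman?** With an assumed share *s* of enrolled women on such drugs, the chance is 1 − (1 − *s*)^50: 64% for *s* = 2%, 92% for 5% and 99.5% for 10%. The documents support no particular *s*.

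**The case against.** The strongest reply is that the gap may seldom matter, and several parts of that reply stand.

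- **Early diagnosis may be uncommon.** The plan describes the 4-16 week OGTT as standard care and places an OGTT inside the wear, so the study OGTT is naturally read as the routine postpartum test. A woman diagnosed earlier by that test would need a second one. The Background puts average compliance with postpartum OGTT testing at 35%. This stands. A drug continued from pregnancy does not depend on that route.
- **The CGM and the OGTT may still agree.** If both are taken under the same treatment, both may be lowered. The disease label then suffers more than their mutual agreement. This stands.
- **HbA1c discordance has another source.** For women tested in the earlier part of the 4-16 week window, 8.7 to 13 weeks reaches back into pregnancy, treated or not. This stands.
- **Records are obtained.** They could reveal a diagnosis or a drug, but no rule acts on what they show. This is only a partial safeguard.

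A reader might also infer three stronger things that the documents do not support. One is that treated women are concentrated at the recruiting clinic: the text is equally consistent with attendance for gestational diabetes care. Another is that treatment begun after the study blood tests must bias the CGM-OGTT relation toward none: the day of the OGTT within the wear is not fixed, and a result, a review, a drug start and a material change in glucose would all have to fall within the 10 days. The third is that a known fraction of the abnormal group carries treated values: no treated share is given anywhere.

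**Conclusion.** The concern holds as a gap in eligibility and data capture. Followed as written, the criteria admit a woman with diabetes diagnosed since delivery or on a glucose-lowering drug at sensor placement, and the classification rule could label a treated woman normal. For a study comparing screening tests this is more than missing detail, because it affects who the result applies to and whether the reference label is right.

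The number affected is unknown. The counts shown rest on the Background's 30% and on assumed values of *k* and *s*. They show only that, with about 15 abnormal women expected, each mislabelled one is about 7% of the group. They do not show that such women will enrol, nor the direction of any bias in CGM-OGTT agreement. The plan should be changed before enrolment, on the ground that the remedy is cheap and the affected women could not be identified from the data now listed.

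**What to change.** 1. Add one exclusion: diabetes diagnosed since delivery, or use of any glucose-lowering drug at sensor placement. Check it in the medical records already obtained to confirm history.
2. Add one medication field: whether a glucose-lowering drug was begun during the wear, and its start date.
3. Keep women who begin such a drug during the wear in the main analysis. Prespecify a sensitivity analysis that leaves out either these women or their sensor days after the first dose, and choose which in advance. Cutting sensor days in the main analysis is not advised, because it would shorten traces mainly in women with abnormal tests.

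**Cost.** One eligibility line, one field that must be asked about at placement and through the wear, and one analysis sentence. A few clinic patients become ineligible, and the abnormal share among those enrolled may fall. On the illustrative counts above, removing 1 treated abnormal woman gives 14/49 = 28.6%, and removing 5 gives 10/45 = 22.2%. The target of 50 can still be met because the exclusion acts before enrolment. The changes concern eligibility, data capture and analysis only; no woman's care changes.

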#### HbA1c, Fructosamine and OGTT data

We will use the glucose levels and HbA1c values as defined by the American Diabetes Association (ADA) guidelines(8) for the diagnosis of normal, prediabetes, and type 2 diabetes. Following the guidelines of ADA, a fasting blood glucose (FBG) below 126 or 2-h blood glucose (2hBG) < 140 mg/dl is considered normal glucose tolerance; FBG of 100-125 mg/dl or 2-h blood glucose (2hBG)  $\geq$  140- 199 mg/dl is classified as prediabetes, and FBG above or equal to 126 mg/dL or 2-h blood glucose (2hBG)  $\geq$  200 mg/dl in a standard oral glucose tolerance test (OGTT) as diabetic. The reference ranges for HbA1c results are:

- No diabetes: below 5.7%
- Borderline/prediabetes: 5.7% to 6.4%
- Diabetes: 6.5% or higher (8)

Fructosamine results may be considered alongside the HbA1c and other tests.

- In non-diabetics with normal albumin, fructosamine levels normally range between 175-265umol/L (micromoles per liter). For people with uncontrolled diabetes, the fructosamine range is 268-870 millimoles per liter (mmol/L). The concentrations of fructosamine corresponding prediabetes and diabetes clinical cut-points of 5.7% and 6.5% for HbA1c, based on percentiles, were 241.4 umol/L (the 77.1 percentile) and 270.2 umol/L (the 96.5 percentile), respectively (36).

Collection of glucose data The blinded glucose monitoring data on glycemia will be retrospectively assessed. The participant data collected from the CGM (Dexcom G7) will be downloaded with the Dexcom G7 reader and uploaded to Dexcom CLARITY

The percentage of time-in-target range, time hypoglycemia, and time hyperglycemia will be reported as either means with standard deviations (SD) or medians with interquartile ranges (IQR), depending on variable distribution. For analyses assessing overnight glycemia, daytime is defined as 5:00 AM to 11:59 PM and nighttime as 12:00 midnight to 4:59 AM

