## Background

Gestational diabetes mellitus (GDM), a complication of glucose intolerance with first recognition in pregnancy, is one of the most common medical problems in pregnancy and strongly linked with the development of type 2 diabetes (T2D) later in life (1–3). Thirty percent of women with GDM will have persistent postpartum dysglycemia, and up to 70% ultimately receive the diagnosis of T2D within 10 years postpartum (4,5). Therefore, postpartum blood glucose screening is important to detect prediabetes and T2D, allowing timely treatment (3-7). For this reason, both the American Diabetes Association (ADA) and American College of Obstetrics & Gynecology (ACOG) recommend a 2-h 75-gram oral glucose tolerance test (OGTT) for all women who had GDM 6–12 weeks after delivery to detect persisting glucose intolerance or diabetes mellitus after pregnancy (8).

Unlike other laboratory tests performed, the OGTT involves several phases, including the need to fast for several hours, to drink a concentrated glucose solution which can induce unpleasant gastrointestinal effects, the collection of three to four blood samples, and the need to remain seated in the laboratory for two to three hours (9). Ingestion of the glucose solution is an important cause of discomfort for patients undergoing an OGTT. Less than half of the women who had GDM comply to the recommendations of postpartum 75-gram OGTT diabetes screening and the majority do not attend any screening for T2D postpartum (10-12). The average compliance rate for postpartum OGTT testing is 35%, largely related to women perceiving the test as inconvenient (13-15). For example, in England, a study which examined postpartum glucose screening rates in women with a history of GDM, using a nationally representative sample from 127 urban and suburban primary care practices, found that just 18.5% of women had glucose screening within six months of birth [16]. Additional studies have identified reasons for non-attendance or non-completion from the perspective of women (17-19); these reasons included: time pressures, lost laboratory forms, not knowing a test was necessary (15,19) feelings of emotional stress while adjusting to a new baby and fear of a T2D diagnosis [(17-19).

The recommended diabetes screening test postpartum is the OGTT, as hemoglobin A1c (HbA1c) is less sensitive to the rapid glycemic variations and

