blood volume changes expected after a recent GDM pregnancy. HbA1c reflects average glycemic exposure over the preceding 2–3 months and is commonly used in people with diabetes to monitor long-term (~3 months) glycemic control (20). Even though the HbA1c is faster, easier, and less expensive to administer, it results in false negative findings 60–70% of the time when the OGTT detects diabetes (21,22). While chronic blood glucose concentrations influence HbA1c levels, many other factors can increase or decrease HbA1c as well, which could lead to questionable HbA1c results and poor alignment with the OGTT. HbA1c levels can be affected by genetic, hematologic, and illness-related factors, especially anemia (23).

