#### STUDY OBJECTIVE

Given the damaging effect of prolonged undetected hyperglycemia, prevention and early diagnosis of T2D is cost-saving and of public health importance. This research study is being done to assess if using a glucose sensor (also known as a continuous glucose monitor or CGM) after childbirth can help identify women who are at risk of developing diabetes after having diabetes during pregnancy or gestational diabetes. Currently, screening for diabetes after childbirth is performed with an oral glucose tolerance test 4-16 weeks after delivery, but this is burdensome and most patients are non-compliant. This study will use a CGM worn on the skin for 10 days. The data from the sensor will be compared to the standard oral glucose tolerance test as well as a HbA1c and fructosamine test. This is a single site study from patients with recent GDM that attended the diabetes clinic at Woman's Hospital. The research team plans to enroll 50 participants aged 18 years or older into the study. Participation in the study is expected to last up to 10 days during the postpartum interval. Study procedures include; 1) consent and screening; and 2) sensor placement and download after 10 days of wear postpartum during which an OGTT, fructosamine and HbA1c test will be administered.

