#### Statistical analysis

Statistical analyses will be performed using SPSS version 15.1 for Windows (SPSS, Inc.; Chicago, IL). Continuous variables will be tested for normality of distribution using the Kolmogorov-Smirnov test. When necessary, non-normally distributed data will be subjected to logarithmic or square-root transformation to obtain a normal distribution where necessary for subsequent analyses. Continuous parameters will be given as means  $\pm$  standard deviations or medians with interquartile ranges (IQR). Results will be presented as mean  $\pm$  standard deviation for normally distributed continuous variables and as medians, with the 25th and 75th IQR for non-normally distributed variables. Categorical data will be presented as percentage. Pearson correlation coefficient ( $r$ ) and the significance for it ( $p$ ) will be calculated between the variables. The chi square test will be used to compare categorical variables. Chi-square test will be used to test differences in percentage proportionality Student t tests will be used to compare normally distributed groups; otherwise, Mann-Whitney rank sum tests will be used. Multiple groups will be compared using Kruskal-Wallis one-way ANOVA with a Dunn's test for pairwise comparisons when appropriate. A two-sided P-value  $< 0.05$  is considered statistically significant.

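### No reference standard is named, and the plan lets HbA1c into the diagnosis while also listing it as a separate test to be compared

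*Combined protocol and SAP*

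**What the plan says.** The section on HbA1c, fructosamine and OGTT data states: "We will use the glucose levels and HbA1c values as defined by the American Diabetes Association (ADA) guidelines(8) for the diagnosis" of normal, prediabetic or diabetic status. It then sets out fasting and 2-hour glucose criteria, and after them a separate HbA1c list introduced by "The reference ranges for HbA1c results are". Fructosamine has its own ranges and may be looked at together with the other tests. The section does not say whether glucose and HbA1c are combined, which prevails, or what happens when they disagree.

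The Study Objective treats the tests as distinct: "The data from the sensor will be compared to the standard oral glucose tolerance test as well as a HbA1c and fructosamine test". The Background says "The recommended diabetes screening test postpartum is the OGTT" and, of HbA1c, that "it results in false negative findings 60–70% of the time when the OGTT detects diabetes". The OGTT is clearly the preferred test, but no section names it as the reference for the analysis.

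The Statistical analysis section plans Pearson coefficients that "will be calculated between the variables", together with chi-square, t or Mann-Whitney, and Kruskal-Wallis tests. It does not say how the groups are formed, and it names no sensitivity, specificity, ROC or agreement measure.

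**The concern.** The only three-level grouping in the protocol is the glycemic status just described, so it is the natural grouping for the Kruskal-Wallis and pairwise comparisons. Read literally, one sentence puts both OGTT glucose and HbA1c into that status.

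If they are merged, HbA1c is compared across groups that it helped to create, which is incorporation bias. The main question also suffers, because CGM metrics would be compared across groups that mix two tests the protocol itself expects to disagree. Fructosamine may be touched too, since two of its quoted cut-points are the values corresponding to HbA1c of 5.7% and 6.5%. Because the combination rule is unwritten, it could be chosen after the discordant results have been seen.

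**Working it through.** The plan gives no accuracy figure or sample-size derivation to reproduce. What follows shows only how far an unstated rule could move the results.

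**Inputs from the documents**
- N = 50: "The research team plans to enroll 50 participants aged 18 years or older into the study" (Study Objective).
- OGTT-positive share p = 0.30: "Thirty percent of women with GDM will have persistent postpartum dysglycemia" (Background), so 50 × 0.30 = 15 positive and 35 normal.
- HbA1c false negatives 60–70% (Background), so sensitivity against the OGTT, Se, is 0.30–0.40. HbA1c is positive in 15 × 0.30 to 15 × 0.40 = 4.5–6 of the 15.

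**Assumptions, not in the documents**
- HbA1c is positive in a fraction f = 5%, 10% or 20% of the 35 OGTT-normal women: 1.75, 3.5 or 7 women.
- A woman is a case if either test is positive.
- The false-negative rate, quoted for diabetes, is applied to any dysglycemia.

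**Formulas under the either-positive rule**
- Cases = 15 + 35f
- Apparent HbA1c sensitivity = (15·Se + 35f) / (15 + 35f)
- HbA1c specificity = 100%, because every HbA1c-positive woman is a case by definition
- Apparent OGTT sensitivity = 15 / (15 + 35f)

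| | OGTT alone | f = 5% | f = 10% | f = 20% |
|---|---|---|---|---|
| Cases | 15 | 16.75 | 18.5 | 22 |
| HbA1c sensitivity | 30–40% | 6.25/16.75 to 7.75/16.75 = 37–46% | 8/18.5 to 9.5/18.5 = 43–51% | 11.5/22 to 13/22 = 52–59% |
| HbA1c specificity | 95%, 90%, 80% for f = 5%, 10%, 20% | 100% | 100% | 100% |
| OGTT sensitivity | 100% | 90% | 81% | 68% |
| OGTT-normal women among cases | 0% | 1.75/16.75 = 10% | 3.5/18.5 = 19% | 7/22 = 32% |

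The last row is what matters for CGM: under these assumptions, 10–32% of the dysglycemic group would have a normal OGTT.

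**Other readings**
- Both tests required: cases fall to 4.5–6, and HbA1c sensitivity, rather than specificity, is forced to 100%.
- f = 0: the either-positive label equals the OGTT label, and nothing is inflated.
- Each test classified by its own cut-points and cross-tabulated: HbA1c keeps its 30–40% sensitivity, and there is no inflation.

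On the same inputs, the unstated rule could therefore move the case count from about 5 to 22 of 50.

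**The case against.** The strongest reply is that no combined rule is written. The section gives each test its own thresholds and its own labels, and a natural reading is that each is categorised separately. On that reading there is no shared label and no bias. This stands as a possible reading, but the sentence that places both tests in the diagnosis equally permits a merged label, and nothing excludes it.

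Second, no HbA1c accuracy estimate is planned, and correlations between continuous CGM, glucose and HbA1c values use no label. Both statements are correct, and the correlations are unaffected. The group comparisons remain exposed, because their groups are undefined.

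Third, the CGM is the test under study and HbA1c only a comparator. That is right, but whatever label forms the groups also determines the CGM comparison.

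Fourth, the figures depend on assumptions. They do: the documents give no HbA1c-positive rate for OGTT-normal women, and a diabetes false-negative rate is paired with a prevalence for any dysglycemia. The figures show direction and possible scale, and are not a forecast.

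**Conclusion.** The point holds as an undefined reference standard with a conditional bias. The plan puts HbA1c into the diagnosis, lists it as a separate test, gives no rule for disagreement and names no reference. If the tests are merged, HbA1c comparisons across groups are partly circular and the CGM groups are mixed. Under the single either-positive scenario, cases go from 15 to about 17–22, apparent HbA1c sensitivity from 30–40% to 37–59%, and specificity to 100%.

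A reader might infer that HbA1c accuracy is inflated by construction, or that the OGTT has ceased to be the reference. The documents support neither. No either-positive rule is stated, separate classification would produce no inflation, and no HbA1c accuracy estimate is planned. The OGTT is treated throughout as the standard test and was never formally made the reference, so it cannot be said to have lost that role.

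**What to change.** In the section on HbA1c, fructosamine and OGTT data, state three things:
- Glycemic status for the analysis, meaning the groups used in the Statistical analysis section, is defined by OGTT fasting and 2-hour glucose alone.
- HbA1c and fructosamine are categorised separately by their own cut-points and never enter that label.
- OGTT and HbA1c categories are cross-tabulated, with agreement and discordance reported.

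The fasting glucose bands there must also be reconciled before the label can be applied: values below 126 mg/dl are listed as normal, while 100–125 mg/dl is listed as prediabetes.

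The cost is a few sentences and one table. No new data are needed. This is an analysis definition only and does not affect clinical care. A woman without a completed OGTT would have no reference status and should be counted as such.

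### The three OGTT categories overlap as printed: every woman who meets prediabetes but not diabetes also meets normal, and no order of precedence is given

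*Combined protocol and SAP*

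**What the plan says.** The section headed HbA1c, Fructosamine and OGTT data takes its glucose and HbA1c values from a cited diabetes guideline "for the diagnosis of normal, prediabetes, and type 2 diabetes". It then prints its own working definitions for the OGTT, all in one sentence:

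- Normal: "a fasting blood glucose (FBG) below 126 or 2-h blood glucose (2hBG) < 140 mg/dl is considered normal glucose tolerance".
- Prediabetes: "FBG of 100-125 mg/dl or 2-h blood glucose" of 140-199 mg/dl.
- Diabetes: "FBG above or equal to 126 mg/dL or 2-h blood glucose" of at least 200 mg/dl.

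The HbA1c categories follow directly: below 5.7%, then "Borderline/prediabetes: 5.7% to 6.4" percent, then 6.5% or higher. These do not overlap.

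The Study Objective section makes the OGTT a comparator for the sensor: "The data from the sensor will be compared to the standard oral glucose tolerance test". On numbers, "Fifty women with a history of GDM will be enrolled". The Statistical analysis section says "Categorical data will be presented as percentage" and plans chi-square tests and comparisons of two or more groups. Neither that section nor any other says which category applies to a woman who meets more than one.

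**The concern.** A three-level classification needs levels that exclude one another. Here the normal rule conflicts with the prediabetes rule in two ways. Its fasting limit of 126 contains the whole prediabetes fasting band of 100-125. Its *or* also lets one unremarkable value outweigh an abnormal one. The prediabetes and diabetes rules overlap as well, because each is met by either value alone.

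Any percentage, chi-square test or group comparison by OGTT category would then depend on the order in which the analyst happens to code the rules. Agreement with HbA1c could be distorted too. A woman with fasting glucose 110, 2-hour glucose 160 and HbA1c 6.0% lies in the plan's own prediabetes range on both tests. If the OGTT rules are applied in printed order, she counts as normal on the OGTT and prediabetes on HbA1c.

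**Working it through.** **Inputs.** All cut-points come from the section on HbA1c, fructosamine and OGTT data, in mg/dl and whole numbers. F is fasting glucose and T is 2-hour glucose.

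- N (normal): F < 126 or T < 140
- P (prediabetes): F 100-125 or T 140-199
- D (diabetes): F ≥ 126 or T ≥ 200

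The plan gives no figure of its own to reproduce, so the check is one of logic.

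**Step 1: the general result.** Not D means F < 126 and T < 200. F < 126 is sufficient for N. So every woman who meets P but not D also meets N, whatever the distribution of glucose.

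**Step 2: all combinations.** The cut-points divide complete pairs into 3 × 3 = 9 bands. The labels met in each band are:

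| | T < 140 | T 140-199 | T ≥ 200 |
|---|---|---|---|
| F < 100 | N | N, P | N, D |
| F 100-125 | N, P | N, P | N, P, D |
| F ≥ 126 | N, D | P, D | D |

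Two bands carry one label, six carry two and one carries three, so 6 + 1 = 7 of 9 are ambiguous. Examples (F/T): 110/160 is normal and prediabetes; 95/210 is normal and diabetes; 130/160 is prediabetes and diabetes; 110/210 is all three.

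**Step 3: effect of coding order.**

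| Rule for ties | Normal | Prediabetes | Diabetes |
|---|---|---|---|
| First match in printed order (N, P, D) | 7 bands | 1 band | 1 band |
| Worst category first (D, P, N) | 1 band | 3 bands | 5 bands |

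In printed order the only band left for prediabetes is F ≥ 126 with T 140-199, which also meets the diabetes rule.

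**Step 4: a more generous reading.** Suppose the *or* in the normal rule was meant as *and* (F < 126 and T < 140). The ambiguous bands fall from 7 to 3. F 100-125 with T < 140 is still both normal and prediabetes. F 100-125 with T ≥ 200, and F ≥ 126 with T 140-199, are still both prediabetes and diabetes. No diabetes band is labelled normal on this reading.

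**Step 5: reconciling the normal rule alone.** If normal is made disjoint from the other two categories and no precedence is added, those same two prediabetes/diabetes bands stay ambiguous (2 of 9). A precedence rule is needed as well.

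**Step 6: scale in women.** Bands are not patients, and the documents give no joint distribution of F and T. If all 50 women have both values and printed order is used, each woman who meets P but not D adds 1/50 = 2 percentage points to normal. Assumed counts of 5, 10 and 15 such women give 5/50 = 10, 10/50 = 20 and 15/50 = 30 points. For orientation, the Background puts persistent postpartum dysglycemia at thirty percent; 0.30 × 50 = 15. That figure is not split into prediabetes and diabetes, so 15 is an upper anchor for the prediabetes count under that assumption, not an estimate of it.

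**The case against.** The strongest reply is that the harm is inferred. The Statistical analysis section names no endpoint based on OGTT category, no sensitivity or specificity analysis and no grouping variable. The Pearson correlations it plans would not change if run on continuous glucose. The plan also names a guideline as its source, so an analyst might apply that source and never code the printed sentence; the misprint is probably a drafting slip. Printed-order coding is only one possible choice, the largest overlap count needs the literal *or*, and the 5, 10 and 15 women are assumptions.

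Much of this is right as a limit on size. The harm does depend on a categorical OGTT analysis being done, and nothing here predicts how many women would be misclassified.

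It does not remove the contradiction. Reading *or* as *and* still leaves the 126 limit in conflict with the 100-125 band. Citing a guideline does not cure explicit cut-points that are printed as following it, and the guideline's text is not in the documents. The three glycaemic categories are also the only multi-level grouping of participants that the plan defines, so they are a natural, though unstated, candidate for its group comparisons.

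**Conclusion.** The concern holds: the OGTT classification is wrong as written and cannot be applied without an undocumented choice by the analyst. The overlap of prediabetes with normal is complete under the printed wording and needs no assumption about the data. Seven of nine bands are ambiguous on the literal reading and three of nine on the generous one. The effect on reported percentages is 2 points per woman affected, assuming 50 complete pairs and printed-order coding; the number of women affected is unknown. Because this is the classification of the comparator test, it should be corrected before any woman is classified.

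**What to change.** For the analysis classification:

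1. Reconcile the normal definition, both its 126 limit and its *or*, with the sentence's own prediabetes range and with the cited guideline. Which cut-off is clinically right is for the sponsor to settle from that source.
2. Add a precedence sentence: *For analysis, each woman is assigned to the worst category met: diabetes, then prediabetes, then normal.* This alone gives one category to every woman with both values; step 1 removes the contradiction in the text.
3. State how a woman with only one of the two glucose values is classified, since the precedence sentence does not settle that.

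A side note for the same section: the 268-870 fructosamine range is printed in mmol/L beside values in umol/L, and the units should be reconciled.

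The cost is a wording correction in one section, with no new data and no extra participants.
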